The primary analysis will fit generalized estimating equations (GEE) with a binary outcome indicating whether a flu vaccine was received during the PCP visit (primary). Following the intention-to-treat framework, patients who do not complete their first scheduled visit will contribute a primary outcome of zero, indicating a flu vaccine was not received during the PCP visit. We will also perform analyses based on a binary outcome that indicates whether a flu vaccine was received 3 months after the first scheduled visit, regardless of whether the visit was completed (secondary). An exchangeable working correlation will be specified at the clinic level for comparison #1 (evaluation of clinic-level nudges) and robust standard errors will be provided, clustered at the clinic level. An independence working correlation and robust standard errors without clustering will be used for comparison #2 (evaluation of individual-level nudges). In sensitivity analyses we will explore alternative specifications for the working correlation structure to examine robustness of parameter estimates and inference. In additional sensitivity analyses, we will censor patients with a PCP visit late in the intervention period (February/March) who are unlikely to complete a flu vaccine beyond March and will therefore not have a full 3 months to obtain a vaccine and examine completion rates among these patients.

We will examine effects of the interventions on overall rates of ordering. We will compare rates of ordering between the three intervention arms: 1) Control, 2) Clinic-level nudges only, and 3) Clinic-level nudges with intensification for high risk. We will fit a GEE with binary outcome indicating whether an order was signed or not. We will fit the model using the weighted and replicated approach¹³ to account for the fact that low-risk patients seen in the clinics that received nudges are consistent with both intervention arms 2) and 3). We will include terms for the main effects of clinic-level and individual-level nudges as well as their interaction. We will test the appropriate linear combinations of the parameters that correspond to pairwise differences between each of the three intervention arms. An independence working correlation with robust standard errors will be

used to account for uncertainty in the weight distribution due to variability in the empirical proportion of high- versus low-risk patients.

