where A_1 is an indicator of whether the patient was seen at an active (1) or control (-1) clinic; A_2 is an indicator of intensive (1) or standard (-1) text messaging (patients who were actually randomized will have only one value for A_2 , while replicated patients will have one 1 and one -1); $A_1 A_2$ is the interaction between the patient’s cluster assignment and their individual-level assignment(s); and X is a vector of all other covariates we want to control for which will at minimum include mean-centered versions of the three variables used in the constrained randomization procedure: 1) clinic size (number of patient visits); 2) baseline clinic risk (proportion of panel deemed high risk); and 3) baseline clinic completion rate (proportion of panel with completed flu vaccination).

We will specify an independence working correlation when fitting the primary GEE model.

Although we expect some amount of correlation amongst observations within clinic, the replicated subject observations should be treated as independent. Fortunately, estimates from GEE models are robust to misspecification of the working correlation structure, meaning they are consistent for the true values even when the working correlation is specified incorrectly. Furthermore, when correlation amongst observations within clinic is low, the efficiency of using an exchangeable working correlation is similar to or worse than when using an independent working correlation. Since we will randomize 45 clinics, we will not use a small cluster correction.² We will use this approach for both the primary and secondary outcome analyses. Given model (1) with effect coding (i.e., -1 and 1 for levels of A_1 and A_2), we have the following:

1. The main effect of A_1 is $2\beta_1$ (i.e., the main effect of clinic-level nudges averaging over the differential effects of standard and intensive texting).
2. The main effect of A_2 given $A_1 = 1$ is $2\beta_2$. This is the comparison of text messaging intensity (standard versus intensive) given clinic-level nudges are active.
3. The comparison of clinic-level nudges with intensive texting versus control is $2\beta_1 + \beta_2$.
4. The comparison of clinic-level nudges with standard texting versus control is $2\beta_1 - \beta_2$.

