We will test each of the four linear contrasts of the parameters estimated from the GEE model. We will use a Bonferroni correction for the first two contrasts, aligning with how the study was powered (i.e., two-sided significance level of 0.025 for the first two contrasts). We will consider contrasts 3 and 4 as exploratory, and thus we will not correct the corresponding p-values for multiple testing. Results will be reported on the odds ratio scale, including 95% confidence intervals. Confidence intervals for contrasts 1 and 2 will incorporate the Bonferroni correction used for the two tests.

Sensitivity Analyses to Evaluate Model Specifications

As a sensitivity analysis, we will restrict the data to high-risk patients at active clinics and estimate the main effect of intensive vs standard text messaging, specifying an exchangeable working

correlation within clinics. As another sensitivity analysis, we will use an exchangeable working correlation at the clinic level after duplicating each clinic's data, assigning one 1 and one -1 for patients without an individual-level assignment, and removing the record for each high-risk patient an intervention clinic corresponding to the opposite of the individual-level randomized assignment that was received. Duplicated clinics will be treated as independent while observations within clinic will be treated as exchangeable. In this way, duplicated records will be treated as independent. Using this approach, we will re-test the main effect of A_1 , i.e., $2\beta_1$, to evaluate sensitivity to specification of the working correlation. We will use a t-distribution with degrees of freedom equal to the number of clinics (47) minus the number of mean model parameters to construct a confidence interval for $2\beta_1$. If the interval does not include 0 (log odds ratio scale) we will reject the null and conclude there is a significant effect of clinic nudges compared to usual care.

Sensitivity Analyses to Evaluate Protocol Deviations

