To examine the effect of the intervention on flu vaccination ordering, a GEE with a binary outcome indicating whether the pended order was signed or cancelled will be fit. The rates of flu vaccination completion will be compared between (1) usual care, (2) clinic level nudge only, and (3) clinic-level nudges with high-risk intensification using the same weighted and replicated approach described for the primary outcome and the mean model given in equation (1). We will again use an independence working correlation for these comparisons and perform sensitivity analyses to assess sensitivity to specification of the working correlation.

Exploratory subgroup analyses will examine the effect of the clinic-level nudge versus usual care among patients who are 1) identified as low-risk for completion and 2) identified as high-risk for completion, and 3) seen at Penn versus UW. For (1), we will restrict the data set to low-risk patients in the active and control clinics. Then, we will fit a GEE model with an indicator for clinic randomized assignment and variables used in the covariate constrained randomization. We will fit the model with a logit link and exchangeable working correlation. For (2), we will subset the data to patients deemed high-risk in both active and control arms, we will fit a GEE model with an indicator for clinic randomized assignment, indicator for individual-level randomized assignment, interaction between the clinic- and individual-level randomized assignments, and variables used in the covariate constrained randomization. We will use the weighted and replicated approach described previously, replicating each high-risk patient in the control arm and assigning them each a weight of 1 while assigning each high-risk patient in the

intervention clinics a weight of 2. We will fit the model with a logit link and independent working correlation. We will test the main effect of the clinic-level nudge and the main effect of standard versus intensive texting. We will test contrasts 1), 3), and 4). For investigating possible effect heterogeneity by health system, we will re-fit models for our primary and secondary outcomes separately on data from Penn and UW.

To investigate potential effect heterogeneity over time, we will fit GEE models for our primary and secondary outcomes with the addition of month and month-by-treatment interactions. The model will take the following form:

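### The exchangeable-correlation check of the clinic effect counts every clinic twice, so as written its standard error is about 0.71 of the clinic-clustered value and its false-positive rate about 11–14% at the 0.025 level

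*SAP*

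**What the plan says.** The SAP's primary model uses an independence working correlation on weighted and replicated data. Under Sensitivity Analyses to Evaluate Model Specifications, it re-tests the clinic effect, 2β1, with an exchangeable structure. Each clinic's data are duplicated, one copy for each texting level. For a high-risk patient at an intervention clinic, only the row matching the assignment received is kept. The SAP then says: "Duplicated clinics will be treated as independent while observations within clinic will be treated as exchangeable", and adds "In this way, duplicated records will be treated as independent".

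The reference distribution and decision rule follow: "We will use a t-distribution with degrees of freedom equal to the number of clinics (47) minus the number of mean model parameters", and "If the interval does not include 0 (log odds ratio scale) we will reject the null". The paragraph does not name a level for the robust variance.

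Three other statements bear on this:
- For the main contrasts, the SAP sets a two-sided level of 0.025 and says "Confidence intervals for contrasts 1 and 2 will incorporate the Bonferroni correction used for the two tests". The contrast 2β1 is contrast 1.
- For the primary model, the SAP says of its 45 clinics that "we will not use a small cluster correction".
- Protocol section 9, Statistical Analysis, says of the clinic comparison that "robust standard errors will be provided, clustered at the clinic level".

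**The concern.** Separating the copies is a sensible way to stop one patient's two rows from entering the same exchangeable block. But in a standard GEE fit, one cluster identifier defines both the working correlation and the units summed in the sandwich variance. If the copy is that identifier, the analysis credits itself with twice as many independent clinics as were randomized.

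This is the SAP's only full-sample exchangeable check of contrast 1. The other exchangeable fit of the clinic effect, under the exploratory analyses ("We will fit the model with a logit link and exchangeable working correlation"), covers low-risk patients only. A check with too small a standard error can declare a clinic effect significant when a correctly clustered exchangeable fit would not, and so appear to support the primary result.

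**Working it through.** **Inputs from the documents.** 47 clinics (SAP, sensitivity section). Six mean-model parameters: β0, β1, β2 and three clinic covariates, so df = 47 − 6 = 41. Two-sided level 0.025. Allocation 2:1. From the protocol's power section: 1385 patients per clinic, ICC ρ = 0.02, and 1000 high-risk patients per intervention clinic.

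**Assumptions.** A 31:16 split of the 47 clinics; completion rates and variation in clinic size as stated in step 5.

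**The plan's own figure.** The SAP gives no standard error or error rate for this test. Its only benchmark is the level, 0.05 / 2 = 0.025.

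**Step 1: overlap of the copies.** A control clinic's copies hold the same 1385 outcomes, so their correlation is r = 1. Each copy of an intervention clinic holds all 385 low-risk patients and about 500 of the 1000 high-risk patients, 885 rows in all. Without weights:
- variance of a copy mean (in units of the outcome variance) = ρ + (1 − ρ)/885 = 0.02 + 0.98/885 = 0.02111
- covariance of the two copy means = ρ + (1 − ρ) × 385/885² = 0.02 + 0.00048 = 0.02048
- r = 0.02048 / 0.02111 = 0.970

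**Step 2: effect on the SE.** The mean of two copies, each with variance V, has variance (V/2)(1 + r). Treating the copies as independent gives V/2. The SE ratio is 1/√(1 + r):
- control clinics: 1/√2 = 0.707
- intervention clinics: 1/√1.970 = 0.712
- both arms combined: 0.709

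The combined ratio stays within 0.707–0.729 for ICCs from 0.001 to 0.05.

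**Step 3: what the t reference recovers.** The critical value at 0.025 is 2.327 with 41 df, against 2.241 for the normal: 2.327/2.241 = 1.038, about 4% wider. The correction needed is 1/0.709 = 1.41, about 41%.

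**Step 4: error rate from duplication alone.** With an otherwise exact t test, the false-positive rate is P(|T41| > 2.327 × 0.707) = P(|T41| > 1.645) = 10.8%. At a nominal 5% it is 16.1%.

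**Step 5: null simulations of model (1).** These used three clinic covariates and exchangeable correlation. The sensitivity paragraph does not say whether the 2/1 weights are kept, so both versions were run.

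- Set A: 8000 trials per setting unweighted, 4000 weighted; ICC 0.01, 0.02 and 0.05; coefficient of variation (CV) of clinic size 0 to 0.8; completion 50%; 45 and 47 clinics.
- Set B: coded separately; 4000 trials per scenario; ICC 0.005 to 0.05, taken as known; completion 40%, with 20% as a check; 45, 47 and 48 clinics. One scenario omitted the covariates.

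| | SE ratio, copies / original clinics | Rejection at 0.025, copies | Rejection at 0.025, original clinics |
|---|---|---|---|
| Set A, unweighted | 0.708–0.712 | 12.9–13.7% | 3.1–4.0% (both Set A rows) |
| Set A, weighted | 0.720–0.727 | 11.1–12.4% | as above |
| Set B | 0.710–0.724 | 11.6–14.3% | 2.9–4.2% |

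If the interval is read as 95%, Set A gives 16.5–19.7% on copies against 5.8–7.2% on original clinics.

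In Set A at ICC 0.02, 47 clinics, CV 0.4 and no weights, the mean SE is 0.060 on copies and 0.084 on original clinics, against a true SD of 0.092. The gap from 0.084 to 0.092 is the uncorrected sandwich, a separate matter.

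**Step 6: the simpler alternative.** An unweighted exchangeable fit on unreplicated rows, clustered by clinic, rejects in 3.3–4.0% of trials at 0.025. Its estimates correlate at 0.998 or more with those from the duplicated data.

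**The case against.** The strongest reply is that the quoted sentence describes only the working correlation, since the paragraph's stated aim is to probe that specification. On that reading the sandwich would still be clustered on the original clinic, as the protocol asks for this comparison, and the problem disappears. Basing the degrees of freedom on 47 also suggests that the authors regard the clinic as the independent unit. Moreover, the SAP does not spell out the sandwich level for the primary model either, so it may seem inconsistent to accept clinic clustering there and not here.

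Part of this stands: the working-correlation reading is possible. But it is unstated, and the text that is there makes each copy an independent unit, with nothing returning the variance to the clinic. The primary model differs, because there the SAP discusses small-cluster correction in terms of 45 clinics, which makes the clinic the cluster.

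Three further points are fair. Duplication alone yields about 10.8%, and the comparator after the fix is 3–4%, not 2.5%. The error rate of a sensitivity test does not inflate that of the primary test, and under the null both tests cannot reject together more often than the primary alone. Finally, the 0.025 level for contrast 1 is already set, so repeating it here is only a clarification.

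**Conclusion.** The specification is wrong as written and should be fixed. The SE of the check is about 0.71 of the clinic-clustered SE (up to 0.727 if the weights are kept), so the interval is about 27–29% too narrow. Its false-positive rate at 0.025 is about 11–14%, against 3–4% with the sandwich on original clinics.

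This rests on the copy serving as the cluster for the variance as well as for the working correlation. The size hardly depends on the assumed completion rate, the ICC, the variation in clinic size, or whether there are 45, 47 or 48 clinics; the documents give all three counts.

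The primary analysis is unaffected and the point estimate of the check remains usable. What cannot be relied on is its interval and the reject-the-null conclusion attached to it.

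**What to change.** State in the sensitivity paragraph that the robust variance is clustered on the original clinic, with both copies under one identifier; the duplicated data may still define the working correlation. Alternatively, fit the exchangeable GEE on unreplicated rows with the clinic as the cluster.

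Keep the t reference of clinics minus parameters, and say that the interval uses the 0.025 level already set for contrast 1. It would help to say at the same time whether the 2/1 weights are kept.

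The cost is about one sentence in the SAP and one cluster-identifier argument in the code. No new data are needed.

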5.1 Design

This study will be a multisite, cluster randomized, pragmatic trial to evaluate the effectiveness of personalized nudges to clinicians and patients, relative to a control, to increase flu vaccination rates among older adults in accordance with CDC guidelines. This will include clinician and patient level nudge interventions, with additional, intensified nudge interventions for patients identified as high risk for not receiving a flu vaccine.

This cluster randomized trial will randomly assign primary care clinics in a 2:1 ratio to either a nudge interventions or control arm using a covariate-constrained randomization.¹⁰ The intervention arm consists of a multi-component nudge intervention for patients and primary care providers (PCPs). Patients at high-risk for non-completion of the flu vaccine will be randomized to an additional intensification nudge (compared with the multi-component nudge intervention alone).

All patients scheduled for a visit at the clinics randomized to the intervention arm will receive a pre-visit text message sent via Way to Health (a HIPAA compliant, approved platform) that informs the patient the flu vaccine has been reserved for them at their upcoming visit. Those patients that do not have a cell phone in the EHR will receive automated voice recording (AVR). For the patient intensification nudge, we will focus on patient subgroups within the clinic intervention arm that were identified through our previous analyses as high risk for not receiving a vaccine: age ≥ 70 , Black race, residence in lower income communities (lowest quartile according to zip code), or no documented history of flu vaccine in the year prior. Patients who meet these criteria will be randomized 1:1 to receive an additional nudge via a bidirectional text messaging intervention versus no additional nudge. We will translate patient text messages for patients who require an interpreter according to their language preferences in the EHR. Translation will be available for Spanish and up to 4 additional languages based on site specific populations and technical capabilities. Our preliminary work identified the following five languages that account for 97.5% of the expected study sample: English, Spanish, Chinese, Vietnamese, and Russian.

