do not show up to the first scheduled clinician visit will be considered enrolled and included in the primary analysis.

--Power Calculations--

For the following power calculations, we used an adjusted Type I error of 0.025 to account for two comparisons: 1) clinic-level nudges versus usual care, and 2) intensification for high-risk patients versus no intensification within practices where clinic-level nudges are provided. Based on retrospective data from our health systems, we will have 85% power to detect a 7-percentage point difference in the flu vaccine completion rate for comparison #1. This calculation assumed N=48 participating clinics across the two sites, an average cluster size of n=1385 patients, and an intracluster correlation (ICC) of 0.02. For comparison #2, we will have at least 99% power to detect a 2-percentage point difference even if the rate of vaccination in the high-risk group is 50%, the most conservative rate with respect to power. This calculation assumed 1:1 individual-level randomization of n=1000 high-risk patients within each of N=32 clinics that will be randomized to receive clinic-level nudges. These power calculations used combined retrospective data from Penn and UW to estimate the average number of patients per clinic and the number of high-risk patients who will be randomized. We expect to have greater power for both comparisons at the replication site which comprises more clinics and patients.

--Statistical Analysis--

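### The exchangeable sensitivity analysis carries its own rejection rule for the clinic-nudge hypothesis, and the SAP does not say that the primary 0.025 test governs if the two disagree

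*SAP*

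**What the plan says.** **Primary test.** Under Analytical Plan for Primary and Secondary Outcomes, the SAP commits to one main model: "We will specify an independence working correlation when fitting the primary GEE model". Contrast 1 is 2β1, the clinic-level effect averaged over texting intensity. The level is a Bonferroni share: "two-sided significance level of 0.025 for the first two contrasts". Intervals for contrasts 1 and 2 are to carry the same correction. Contrasts 3 and 4 are called exploratory and are left uncorrected.

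**Second test.** Under Sensitivity Analyses to Evaluate Model Specifications, each clinic's data are duplicated, an exchangeable working correlation is used, and 2β1 is tested again. The interval uses a t-distribution with 47 minus the number of mean-model parameters as degrees of freedom. If it excludes 0, "we will reject the null and conclude there is a significant effect of clinic nudges compared to usual care". The paragraph gives its purpose as checking sensitivity to the working correlation. It does not restate the interval's level or say what follows if this result and the primary one differ.

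**Protocol.** Section 9, Power Calculations, uses the same split: "we used an adjusted Type I error of 0.025 to account for two comparisons". Section 9, Statistical Analysis, specifies an exchangeable working correlation at clinic level as the primary analysis of comparison #1.

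**The concern.** One hypothesis has two written tests and one allotment of alpha. The 0.025 share covers one test of contrast 1 and one of contrast 2, with nothing set aside for a second test of contrast 1. The only explicit reject-and-conclude sentence in the SAP belongs to the sensitivity analysis, and it is worded as a conclusion about the hypothesis.

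The case that matters is a primary test that misses 0.025 and an exchangeable interval that excludes 0. Read literally, the SAP then tells the authors to conclude that there is an effect. Because the protocol had the exchangeable GEE as primary, that choice would be easy to defend afterwards. A pre-specified decision rule should settle this before the data are seen.

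**Working it through.** **1. The allotted level.** 0.05 / 2 = 0.025 for each of two contrasts, as stated.

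**2. The design used that level.** The protocol says "we will have 85% power to detect a 7-percentage point difference in the flu vaccine completion rate for comparison #1". Its inputs are: "This calculation assumed N=48 participating clinics across the two sites, an average cluster size of n=1385 patients, and an intracluster correlation (ICC) of 0.02". With 2:1 allocation, 48 clinics give 32 and 16.

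- Design effect: 1 + (1385 − 1) × 0.02 = 28.68.
- Effective sizes: control 16 × 1385 / 28.68 = 772.7; intervention 32 × 1385 / 28.68 = 1545.3.
- Power = Φ[(0.07 − 2.241 × SE0) / SE1], where SE0 is the pooled and SE1 the unpooled standard error of the difference. The cut-off for two-sided 0.025 is 2.241.
- Example, control rate 0.35: pooled rate (0.35 + 2 × 0.42) / 3 = 0.3967, SE0 = 0.02155, SE1 = 0.02126, power = Φ(1.02) = 84.6%.

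The protocol gives no control rate, so it was varied from 0.30 to 0.60. Power is 86.8% at 0.30, 83.2% at 0.40, 82.6% at 0.45, 82.9% at 0.50 and 85.8% at 0.60. The stated 85% is approximately reproduced. At alpha 0.05 the same inputs give 89% to 92%, so 0.025 is the level that fits.

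**3. Error if either test may reject.** Let Z1 be the primary statistic and Z2 the sensitivity statistic, jointly normal under the null with correlation r. The error for contrast 1 is P(|Z1| > c1 or |Z2| > c2), with c1 = 2.241.

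The documents do not give r. It depends mainly on how much clinic sizes vary, which is also not given. Two approaches gave the assumed range:

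- Size-weighted against inverse-variance-weighted clinic contrasts (45 clinics, 30:15, mean size 1385, ICC 0.02, log-normal sizes with coefficient of variation 0.4 to 1.0): r = 0.94 to 0.76.
- A null simulation of both GEE analyses (coefficient of variation 0.3 to 0.9, 40% vaccination rate and 72% high-risk assumed, 6000 runs each): r = 0.97 to 0.82.

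| r | both at 0.025 (c2 = 2.241) | 97.5% interval, t on 41 df (c2 = 2.327) | 95% interval (c2 = 1.960) |
|---|---|---|---|
| 0.97 | 3.1% | 2.9% | 5.1% |
| 0.94 | 3.4% | 3.1% | 5.4% |
| 0.90 | 3.6% | 3.3% | 5.6% |
| 0.82 | 4.0% | 3.6% | 6.0% |
| 0.76 | 4.1% | 3.8% | 6.3% |

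The second and fourth columns treat each test as exactly sized. The third applies the SAP's t cut-off within the same normal model; 41 is 47 minus six parameters (intercept, A1, A1A2 and the three minimum covariates).

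**4. Effect on the two-contrast total.** Adding 0.025 for contrast 2 to the second column bounds the total at 3.1% + 2.5% = 5.6% to 4.1% + 2.5% = 6.6%, against the intended 5%.

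**5. How often the second test rejects alone.** In the simulation, with the variance clustered on the original clinics and the second test at nominal 0.025, it rejected where the primary did not in 0.6% to 1.2% of null trials.

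**The case against.** The strongest reply is that the hierarchy is already in the SAP. A single primary model is named, the 0.025 level is attached to contrasts from that model, and the disputed sentence falls under a sensitivity heading with a stated robustness purpose. It can be read as explaining how an interval serves as a test. Sensitivity analyses are not ordinarily given a share of alpha. This stands to a large extent: a reader might infer that the SAP adopts a rule under which either test wins, or that Bonferroni control is lost. The documents do not support that. They leave the point open, and error rises only if the second rule is used after the primary test fails.

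The second reply is that the level is not truly missing. The sensitivity interval is for 2β1, which is contrast 1, and the SAP says that intervals for contrast 1 carry the Bonferroni correction. This also stands: 97.5% is the natural reading, and the 95% column should not be taken as the plan's intention. It does not remove the point, because a second test at 0.025 is still a test without an allotment.

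The third reply is that the size depends on assumptions and is small, and that the t cut-off is stricter than the primary test's normal one. This stands. With identical estimates and standard errors, the second test could not reject where the primary failed.

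A reader might also infer much larger error because the SAP treats duplicated clinics as independent. If the robust variance did so too, the standard error could be too small by up to √2, and a nominal 0.025 test would have error of about 11%. The SAP does not say how that variance is clustered. This is a separate question and no part of the size claimed here.

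What remains is that the sentence directs a conclusion about the primary hypothesis, and nothing in the SAP subordinates it.

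**Conclusion.** The concern holds in limited form. The sensitivity paragraph states a confirmatory rule for a hypothesis already tested at its full 0.025, with no statement of which result governs. If the rule were used as a second route to success, error for contrast 1 would be about 3-4% instead of 2.5% with the natural 97.5% interval, and about 5-6% only with a 95% interval.

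The figures rest on assumed correlations of 0.97 to 0.76, hence on assumed clinic-size variation, and on each test holding its own level. That last condition is not assured: in the simulation the uncorrected primary test rejected in 4.7% to 7.6% of null trials at nominal 2.5%, which is a separate matter. The inflation is modest, but the wording should be changed because the remedy costs almost nothing.

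**What to change.** In the SAP, under Sensitivity Analyses to Evaluate Model Specifications, delete the sentence that rejects the null and draws a conclusion. Put in its place: *The conclusion for contrast 1 rests only on the primary model at two-sided 0.025. The exchangeable estimate is reported with its 97.5% interval as supportive evidence of robustness and does not change that conclusion.* This fixes the interval's level and settles which working correlation governs, given the protocol's different specification.

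The cost is one sentence. The analysis is still run and reported in full; what is given up is its ability to support a claim on its own.
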